11 and legibility.

12
13 All records which support case reports of this study must be retained in the files of the
14 principal investigator.

15
16 **X. INFORMED CONSENT**

17
18 Each subject must voluntarily sign the informed consent form before participating in this
19 study. Obligation for obtaining the informed consents for both studies of each subject is
20 assumed by the investigator. The study protocols and informed consent forms must be
21 approved by the investigator's IRB. Each original will be retained by the investigator and
22 a copy will be given to each patient.

23
24 **XI. PATIENT CONFIDENTIALITY**

25
26 All reports and communications relating to patients in the study will identify each subject
27 only by the patient's initials and by the patient's study number. The investigator agrees to
28 retain complete patient identification on the confidential patient follow-up form, which
29 will be used for the purpose of long-term follow-up if needed. This information will be
30 treated with strict adherence to professional standards of confidentiality.

1

2 Case report forms will be reviewed for completeness and acceptability by the principal
3 investigator or designee at the study site. Portions of the patients medical records
4 pertinent to the study will be reviewed by these personnel and possibly by FDA personnel
5 to assure accuracy.

6 **XII. USE OF INFORMATION AND PUBLICATION**

7

8 To allow for the use of the information derived from this clinical study and to insure
9 complete and thorough analysis, the investigator is obligated to provide the NIAID with
10 complete test results and all data developed in this study. Included in the data will be
11 results of testing for concordance for seropositivity by a second laboratory. Should the
12 investigator choose to publish the results of this study, a copy of the manuscript will be
13 provided to NIAID at least 30 days prior to the date of submission to the intended
14 publisher.

15

16 **XIII. COMPLETION OF STUDY**

17

18 The investigator will complete and report this study in satisfactory compliance with the
19 protocol within 12 months of final data collection.

20

21 If, at the completion of the study, the protocol treatment is found to be effective, patients
22 who have received the placebo will be offered the study treatment regimen (30 days of
23 intravenous Rocephin, 2 grams per day, followed by 60 days of oral doxycycline, 200mg

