- 11 7. Patients who have comorbid disease(s) that could account for symptoms of
12 chronic Lyme disease (a, b, and c above). Examples include severe clinical
13 depression, rheumatic illness such as rheumatoid arthritis or SLE, other potential
14 causes of radiculopathic pain such as intervertebral disc disease, etc.
- 15 8. Patients who have a serious comorbid disease (e.g. hematologic malignancy,
16 cirrhosis, metastatic cancer, etc.) or an active infection (e.g., HIV, tuberculosis,
17 etc.).
- 18 9. Patients who are receiving chronic medication therapy that could interfere with
19 the evaluation of symptoms in a, b, c above (e.g., narcotic analgesics, prednisone
20 ≥ 10 mg/day).
- 21 10. Patients who cannot tolerate or do not have adequate venous access for an
22 indwelling venous access catheter or are at increased risk of acquiring an
23 intravenous catheter related infection.
- 24 11. Patients who are pregnant, lactating, or unable to use birth control measures
25 during the treatment period of the study.

1 12. Patients who have previously enrolled in this study.

2 13. Patients who have positive PCR for *Borrelia* DNA in plasma or cerebrospinal
3 fluid at the time of initial evaluation for this study.

4 **VI. STUDY PROCEDURES**

5
6 A. Initial Evaluation Procedures (Up to Two Weeks Prior to Dosing)

7
8 Within four weeks prior to administration of antibiotics or placebo, the following will be
9 obtained to assess compliance with the subject selection criteria outlined in Section V.
10 Patients will have a complete history and physical examination including detailed
11 neurologic examination and evaluation of tender points at 18 sites. Standardized history
12 and physical examination will be used to assess each patient for collection of
13 demographic data, a history of exposure to ticks in geographic regions with endemic *B.*
14 *burgdorferi* infection, clinical manifestations of acute Lyme disease, clinical
15 manifestations of chronic Lyme disease, prior treatment, history of previous serologic
16 tests for Lyme disease (although serologic status will be determined in the central
17 laboratory at the time of initial testing on entry to the study), medication allergies, recent
18 (last 2 months) and current medications. If the patient meets all the inclusion criteria and
19 none of the exclusion criteria, the study protocol will be explained and the patient will be
20 offered participation in the study.

21

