16 Personality Inventory is considered indicative of depression.

17 8. For patients whose persistent symptoms are of peripheral neuropathy including
18 paresthesias or radicular pain, a detailed electromyographic examination of limb
19 and paraspinal muscles will be performed with concentric needle electrodes. ²⁵
20 Motor nerve and sensory-nerve conduction studies of the medial ulnar, peroneal,
21 and tibial nerves will be performed with 10-mm surface recording and stimulating
22 electrodes.

23 9. Testing for immune response to *B. burgdorferi* antigens in serum ²⁶ and
24 cerebrospinal fluid ²⁷.

25 10. Cerebrospinal fluid and plasma specimens from patients enrolled in this study will
26 be tested for the presence of *B.burgdorferi* DNA that encodes outer-surface protein
27 (OspA). After extracting the DNA from the fluid, the samples are tested with a
28 primer-probe set (called OspA 2,4) that targets a C-terminal portion of OspA (see

1 methods in the technical proposal). The samples are then amplified by 45 cycles of
2 PCR. The amplicons are resolved by agarose gel electrophoresis and stained with
3 ethidium bromide. After transfer to a nitrocellulose membrane, the membrane is
4 hybridized with a P32-labelled DNA probe by southern blotting. The membrane is
5 then exposed to autoradiography for 6-72 hr. Positive and negative controls are
6 used throughout this procedure.

7 11. Culture. All CSF samples will be cultured for the presence of *B. burgdorferi* in
8 BSK II medium and monitored by dark field microscopy for 6 weeks. Details of
9 the methods are contained in ²⁸.

10 12. For those women of child bearing age, urine pregnancy test will be performed.
11 Menstrual cycle dates will be recorded in the patient diary.

12 13. Informed consent obtained in writing.

13 14. Serologic test for antibodies against *Babesia microti* ²⁹.

14 15. Urine sample for subsequent testing of *B.burgdorferi* urine antigen ³⁰.

15 **B. Patient Number Assignment**

16

17 After the investigator determines that the patient qualifies for the study, explains the
18 nature of the study to the patient, and obtains informed consent documented in writing,
19 the investigator or designee will assign each patient to the appropriate stratum based on
20 the duration of their symptoms of chronic Lyme disease (less than four years, four to less
21 than eight years, or eight to less than twelve years) and then assign a patient number for

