22 the study to the patient in numerical sequence within that stratum. The
23 investigator/designee will record the patient's initials and date of administration of the
24 first dose of the study medication on the case report form.

25

1 C. Medication Administration

2
3 The investigator will be given a blinded infusion bag or a pre-mixed 30 ml. syringe which
4 contains the study drug required for the patient's first infusion. The treatments
5 (ceftriaxone 2.0 grams in 100 ml. of 5% dextrose in water or placebo consisting of 100
6 ml. 5% dextrose in water with multi-vitamin to match the study medication for color) will
7 be contained in identical looking infusion bags that will have patient numbers noted on
8 the label and will be infused by gravity over 15 minutes. Syringes (containing either
9 ceftriaxone 2.0 grams in 30 ml. of 5% dextrose in water or placebo consisting of 30 ml.
10 5% dextrose in water with multi-vitamin to match the study medication for color) will
11 have patient numbers noted on the label and will be infused by I.V. push over 2-4
12 minutes. Approximate doses of multi-vitamin for color matching are:

13

	Infusion bag	Syringe	
14			
15	Ascorbic Acid	10 mg	3 mg
16	Vitamin A	200 mg	60 mg
17	Vitamin D	20 mg	6.0 mg
18	Thiamin	1.0 mg	0.3 mg
19	Riboflavin	0.8 mg	0.06 mg
20	Pyridoxine	0.3 mg	0.09 mg
21	Niacinamide	2.0 mg	0.6 mg
22	Vitamin E	0.01 I.U.	0.03 I.U.

23 All first infusions of study medication will be monitored by one of the
24 physician/investigators. Subsequent infusions will be made under the supervision of the
25 principal investigator or designee (study nurse). We expect that most of these infusions
26 will take place in the patient's home. Following completion of the course of parenteral
27 therapy patients will be dispensed oral medication containing doxycycline 100 mg. or
28 identically appearing placebo (dextrose) which will be administered as one capsule every
29 12 hours for 60 consecutive days. Patients will be instructed that the oral medication may
30 be taken with or without food.

1 Patient Instructions

2
3 All patients will receive instructions regarding possible side effects of treatment. Known
4 side effects from ceftriaxone include but are not limited to: rash, diarrhea, GI upset,
5 cholestasis, and anaphylaxis; known side effects from doxycycline include but are not
6 limited to rash, photosensitization, diarrhea, GI upset, anaphylaxis, embryotoxicity and

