7 teratogenicity. Patients will also be instructed on signs of intravenous catheter infection.
8 Patients will be able to reach the principal investigator or designee at any time to discuss
9 any symptoms they may be experiencing during the administration of antibiotics or
10 placebo.

11
12 E. Evaluations During Dosing Period

13
14 Ceftriaxone/Doxycycline or Placebo(Study Days 1 - 90).

- 15
16 1. Vital Signs Vital signs will be obtained on Days 1, 3, 5, 9,13,17, 21, 25 and 30.
17
18 2. Laboratory Tests Blood samples (15ml) will be obtained on Days 3, 5, 13, 21, 30,
19 45 and 75. CBC and liver function (as described in Section VI. A.4) will be
20 performed on samples from days 5, 13, 21, 30, 45 and 75 for safety monitoring.
21 Portions of these samples (from days 3, 5, 21 and 45) will be used for serial PCR
22 testing to detect the appearance of borrelial DNA during treatment. Aliquots from
23 these samples will also be stored at -70C as part of a specimen bank in patients
24 with chronic Lyme disease for future studies. Urine samples (10 ml) will be
25 collected on days 3, 5, 13, 21, 30, 45, and 75, and stored in aliquots at -70C.
26 These specimens will be used for serial antigen testing and as part of the specimen
27 bank for future studies of patients with chronic Lyme disease. No additional blood
28 studies will be obtained from these patients except as noted below.
29

1 3. Compliance The patient will be queried at each visit regarding all medications
2 taken, including all background medication. The information will be recorded in
3 the Case Report Form.

4

5 A capsule count for the trial medication will be done at the day 45 and day 75
6 visit to monitor compliance. All unused medication should be returned to the
7 Coordinating Center upon completion of the study. Any deviation from the
8 regimen designated by the protocol must be explained; the patient should explain
9 any apparent non-compliance. This will be recorded in the Case Report Form.

10

11 F. Post-Treatment Evaluations

12

13 Follow up evaluation by one of the physician investigators will occur at the completion of
14 intravenous therapy (day 30) and then at the completion of oral therapy (day 90). Post-
15 treatment evaluations will follow on days 180, and 360. At each of these visits all
16 patients will repeat the SF™ 36 Health Survey and the Fibrositis [fibromyalgia] Impact
17 Questionnaire. Physical examination with standardized recording of findings will also be

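### The only scheduled pregnancy test can be up to 44 or 58 days old at the first dose of doxycycline, which the protocol itself calls teratogenic

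*Protocol*

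**What the plan says.** Item 12 of the Initial Evaluation list (Protocol VI.A) contains the only pregnancy test: "For those women of child bearing age, urine pregnancy test will be performed". The same item adds a diary: "Menstrual cycle dates will be recorded in the patient diary".

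Section VI.A gives two windows for this evaluation. Its heading reads "A. Initial Evaluation Procedures (Up to Two Weeks Prior to Dosing", while its first sentence begins "Within four weeks prior to administration of antibiotics or placebo, the following will be".

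The Patient Instructions in section VI give the known risks of doxycycline as including but not "limited to rash, photosensitization, diarrhea, GI upset, anaphylaxis, embryotoxicity and" "teratogenicity. Patients will also be instructed on signs of intravenous catheter infection". Neither reproductive risk appears in the list for ceftriaxone.

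Section VI.C says that after the intravenous course "therapy patients will be dispensed oral medication containing doxycycline 100 mg. or" a matching placebo, and sets no pregnancy condition. Section VI.E.2 limits on-treatment safety testing to blood counts and liver function. It also collects urine on several days, including 30, 45 and 75, and freezes it for antigen testing and a specimen bank. Section VI.F places a physician visit at day 30 and adds no pregnancy test.

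Exclusion criterion 11 (V.B) bars "Patients who are pregnant, lactating, or unable to use birth control measures" during the treatment period.

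**The concern.** The one test is tied to the start of ceftriaxone, for which the protocol names no reproductive hazard. The drug for which it does name one starts a month later with no test in front of it. A negative result at screening says nothing about a conception after screening. If contraception fails in that interval, the schedule as written allows an early, unrecognised pregnancy to be exposed to doxycycline for up to 60 days.

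Day 30 matters because it is the last point at which exposure can be prevented rather than cut short. A physician visit, safety blood tests and a urine collection already take place then.

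**Working it through.** The protocol states no figure for the age of the test at the first oral dose, so there is nothing to reproduce. The interval follows from its schedule.

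**Inputs**
- Screening window: 14 days (VI.A heading) or 28 days (VI.A text).
- Intravenous phase: 30 consecutive days (section III), days 1 to 30 when the first infusion is day 1.
- Oral phase: 60 consecutive days at 200 mg/day in two capsules (section III), days 31 to 90.
- Patients: 194, randomized 1:1 (section III).

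**Maximum age of the only test at the first doxycycline dose (day 31)**

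Age = screening window + 30 days.

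| Window | At first oral dose | At last oral day (day 90, 59 days later) |
|---|---|---|
| 14 days | 14 + 30 = 44 days | 44 + 59 = 103 days |
| 28 days | 28 + 30 = 58 days | 58 + 59 = 117 days |

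With a test on day 30 the age at the first oral dose is 31 − 30 = 1 day.

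**Exposure that a positive day-30 test could avert, as a maximum**
- 60 days × 2 capsules = 120 capsules.
- 60 days × 200 mg = 12,000 mg = 12 g of doxycycline, for a woman on active drug.
- With 1:1 allocation about half of the women testing positive would be on placebo, so the average ceiling per positive test is 0.5 × 12 g = 6 g.

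**Number of tests, upper bound (as if every patient qualified)**
- Day 30 only: 194 × 1 = 194.
- Days 30, 45 and 75: 194 × 3 = 582. The longest gap between tests is then 75 − 45 = 30 days.

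**Effect on the analysis sets (VIII.B)**

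The secondary analysis needs at least 75% of therapy. Counted in days, that is 0.75 × 90 = 67.5 days.

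| Stopped at day | Share of 90 treatment days | In the secondary analysis? |
|---|---|---|
| 30 | 30/90 = 33% | No |
| 45 | 45/90 = 50% | No |
| 75 | 75/90 = 83% | Yes |

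The primary intent-to-treat analysis keeps all of them.

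**Existing safeguards against the gap**
- Exclusion 11 makes conception less likely but cannot detect a contraceptive failure.
- The diary records dates, but no review or action rule is stated.
- Side-effect instructions, access to the investigator, adverse-event monitoring (VII.A) and the power to discontinue a patient (VII.C) work only once someone suspects a pregnancy.
- The day-30 visit specifies questionnaires and a physical examination, not pregnancy status.
- Immediate reporting of a congenital anomaly (VII.A) comes after the harm.

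**The case against.** The strongest reply is that the protocol contains no error here. It manages pregnancy risk in layers: contraception through the whole treatment period, a diary placed beside the screening test and evidently meant for the same purpose, explicit warnings to patients, and staff contact on nine days up to day 30. A woman who conceived soon after screening would ordinarily have a missed period to record before or around day 30. The figures are also stacked maxima. The 44 or 58 days need screening on the earliest permitted day, and the 60 days need a pregnancy that goes unrecognised to day 90 despite visits on days 45 and 75. Half of the positive women would be on placebo. A day-30 test does nothing for conceptions during the oral phase and can miss a very recent one. Finally, the consent pages, case report forms and diary are not available, and dispensing on day 30 is an inference from the end of the intravenous course.

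Much of this stands as a limit on size. The figures are maxima, the placebo share halves the average ceiling, and the expected number of cases is small. It does not remove the point. Each existing layer is an entry criterion or depends on someone noticing, and none requires a check before oral drug is handed out. The diary comes closest, but the protocol attaches no action to it. Instructions in the unseen papers could help a patient report a pregnancy, but the clinical schedule, which is shown, contains no retest.

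**Conclusion.** The concern holds. The single scheduled pregnancy test can be up to 44 days old (two-week window) or 58 days old (four-week window) at the first dose of a drug the protocol names as embryotoxic and teratogenic, and no retest is required before dispensing. The day count assumes uninterrupted dosing, with the first infusion on day 1 and the first oral dose on day 31.

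No number of pregnancies is claimed, because the protocol gives neither the number of women of childbearing age nor a contraceptive failure rate. This is a participant-safety point with no bearing on sample size, power or alpha. The change should be made because the harm is serious, the protocol itself recognises it, and an existing visit offers a cheap way to prevent part of it.

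**What to change.** Add the following to VI.C and VI.E for women of childbearing age in both groups:

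- Run a urine pregnancy test on the fresh day-30 sample before it is frozen, and dispense oral study drug only if it is negative.
- Optionally repeat the test on the day-45 and day-75 urine, accepting that these can only shorten an exposure.
- On any positive result, do not start oral drug, or stop it. Keep the patient in follow-up and in the intent-to-treat analysis, and record the pregnancy and its outcome on the case report form.
- No unblinding is needed at day 30, because oral drug is withheld in the same way in both groups.

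The two windows in VI.A should be reconciled at the same time, since they are the source of the two figures.

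The cost is one urine test per eligible woman on a sample already taken and one case report form entry, with no added visit, sample or staff. There are three small downsides. A false positive would occasionally delay oral dosing. A very recent conception can still be missed. A woman stopped at day 30 or 45 leaves the secondary analysis of patients with at least 75% of therapy.

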18 recorded. Repeat neuropsychological testing to provide measures of immediate and
19 delayed memory, conceptualization, copying, perceptual discrimination, depression and
20 language will be performed at 90, 180 and 360 days. While all tests will be administered
21 at the 90 day visit, only those tests which are not affected by "learning" will be repeated
22 at 180 and 360 days (see methods for details). Blood (10cc) and urine will be collected at
23 90, 180 and 360 day follow up visits. Samples will be compared to baseline for an IgG
24 response to borrelial antigens. In those patients in whom initial CSF is abnormal for any
25 of the baseline parameters, follow-up lumbar puncture and CSF evaluations will be
26 performed on day 90. Since patients will be enrolled over the first 3.0 years we will have
27 the opportunity for long term follow-up. Therefore, we will also do telephone follow-up
28 every 6 months of patients after the 360 day follow visit.

29

1 **VII. MANAGEMENT OF INTERCURRENT EVENTS**

2
3 **A. Adverse Events**

4
5 Throughout the duration of the study, the investigator will monitor each patient for
6 evidence of drug intolerance and for the development of clinical and laboratory evidence
7 of an adverse event. All adverse events, including those which have previously been
8 reported as attributable to ceftriaxone, doxycycline or the presence of an intravenous
9 catheter or which are judged by the investigator to be related to the therapy will be
10 recorded on the case report form and followed to a satisfactory conclusion. The
11 description of the adverse event will include the date, time of onset, duration, severity,
12 etiology, relationship of the event to the study drug and any treatment or action required.
13 The investigator will rate the severity of the adverse event according to the following
14 definitions:

15
16 **Severity:**

- 17
18 1. **Mild**: The adverse event is transient and easily tolerated by patient.
19
20 2. **Moderate**: The adverse event causes the patient discomfort and interrupts the
21 patient ' s usual activities.
22
23 3. **Severe**: The adverse event causes considerable interference with the patient's
24 usual activities, and may be incapacitating or life threatening.
25

26 **Likelihood that event is related to medication:**

- 27
28 1. **Concurrent Condition**: An event, illness or effect of another drug not related to

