29 study drug (e.g., has not been reported for this drug, transient, or has no temporal
30 relationship to study drug, or has a definite alternative etiology).

1

2 2. Remote ADE: An adverse event not commonly associated with this drug class,
3 has little or no temporal relationship to the study drug, and a probable alternative
4 etiology exists.

5

6 3. Possible ADE: An adverse event not commonly associated with this drug class,
7 has a temporal relationship to the study drug, and a possible alternative etiology
8 exists.

9

10 4. Probable ADE: An adverse event commonly associated with this drug class, has a
11 temporal relationship to the study drug, lessened after the drug was discontinued,
12 and no other etiology is apparent.

13

14 5. Definite ADE: An adverse event commonly associated with this drug class, has a
15 temporal relationship to the study drug, reappeared on rechallenge, and no other
16 etiology is apparent.

17

18 All deaths and serious adverse experiences which occur during the study or the post-
19 therapy period, regardless of treatment group or relationship to drug, must be reported
20 IMMEDIATELY BY TELEPHONE to the Clinical and Regulatory Affairs Branch
21 (CRAB), DMID, NIAID. A serious adverse experience includes, but is not necessarily
22 restricted to, events which are: [a] fatal; [b] life-threatening or potentially life-
23 threatening; [c] permanently disabling; [d] an event requiring hospitalization; or [e] a
24 congenital anomaly, cancer, or the result of overdose. It should be emphasized that,
25 regardless of these criteria, any additional adverse experience which the investigator
26 considers significant enough to merit immediate reporting should be so reported.

27

28 Every three months a report tabulating the adverse events by masked treatment
29 assignment will be prepared by the statistical unit and transmitted in confidence to the to

1 Medical Officer, NIAID, and the DSMB Safety Officer. These reports will include all
2 events and indicate for each whether or not they are considered attributable to the study
3 medication.

4
5 B. Concomitant Drugs

6
7 If administration of any concurrent medication is necessary during the course of this
8 study, dosage information, dates of administration, and indication for use must be
9 reported on the appropriate case report form. Administration of additional antibiotics to
10 treat intercurrent infectious diseases is acceptable provided the agent is not administered

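### The adverse-event causality scale treats transience and novelty as signs of no relationship and is neither exhaustive nor mutually exclusive, so the attribution flag in the three-monthly safety report is unreliable

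*Protocol*

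**What the plan says.** Protocol section VII.A gives two scales for each adverse event, severity and likelihood of relationship to medication.

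- **Severity, Mild:** "The adverse event is transient and easily tolerated by patient".
- **Concurrent Condition (level 1):** "An event, illness or effect of another drug not related to" study drug. The examples begin "study drug (e.g., has not been reported for this drug, transient, or has no temporal" relationship, and end with a definite alternative etiology. They are joined by *or*.
- **Remote (level 2):** an event uncommon for the drug class that "has little or no temporal relationship to the study drug, and a probable alternative" etiology.
- **Possible (level 3):** "Possible ADE: An adverse event not commonly associated with this drug class", with a temporal relationship and a possible alternative etiology.
- **Probable (level 4):** an event common for the class, "temporal relationship to the study drug, lessened after the drug was discontinued", with no other apparent etiology.
- **Definite (level 5):** as Probable, but with recurrence on rechallenge in place of improvement after stopping.

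The three-monthly report to the Medical Officer and the DSMB Safety Officer must cover all "events and indicate for each whether or not they are considered attributable to the study" medication. No text says which of the five levels count as attributable. In the Patient Instructions of section VI the protocol lists the reactions that it expects, for example "side effects from ceftriaxone include but are not limited to: rash, diarrhea, GI upset".

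**The concern.** Two of the examples for the unrelated level are not evidence on causation. A drug reaction can be short, and a reaction not seen before is by its nature unreported. Because Mild is defined by transience, every Mild event meets one of these examples. The rash, diarrhea and GI upset that the protocol expects meet it whenever they are graded Mild.

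The remaining levels do not cover the ground between them. Remote and Possible admit only events that are uncommon for the class. Probable and Definite admit only common ones, with no other cause and with a positive dechallenge or rechallenge. An investigator holding a typical event with a doubtful alternative cause has no level to choose.

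At stake is the attribution column that two safety readers receive every three months. Investigators assign causality at the site from these definitions, so a later analysis plan cannot repair the ratings.

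**Working it through.** The protocol gives no figure to reproduce here, so the check applies the five definitions literally to every combination of their own criteria.

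**Criteria, all from section VII.A:** common for the class (yes/no); transient (yes/no); temporal relationship (yes, or little/none); alternative etiology (none, possible, probable, definite); course off drug (not improved, improved, improved and recurred on rechallenge). Profiles: 2 × 2 × 2 × 4 × 3 = 96.

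**Assumptions:** the event has been reported for the drug before, and each example under level 1 is taken as sufficient.

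**Profiles of interest:** temporal relationship present and no definite alternative: 2 × 2 × 1 × 3 × 3 = 36, of which 18 are non-transient and 18 transient.

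*Non-transient, 18 profiles:*

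| Alternative etiology | Common for class (3 per row) | Uncommon (3 per row) |
|---|---|---|
| None | 2 fit Probable and/or Definite; 1 (not improved) fits nothing | 3 fit nothing |
| Possible | 3 fit nothing | 3 fit Possible |
| Probable | 3 fit nothing | 3 fit nothing |
| No level | 1 + 3 + 3 = 7 of 9 | 3 + 0 + 3 = 6 of 9 |

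In total 7 + 6 = 13 of 18 have no level. Examples are a typical reaction that has not lessened off drug and has no other cause, a typical reaction with a possible alternative cause, and an atypical event with clear timing and no alternative cause, even if it recurs on rechallenge.

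*Transient, the same 18 profiles:* all now meet level 1. The 13 that had no level become unrelated only. The other 5 (2 common with no alternative, 3 uncommon with a possible alternative) are unrelated and also Possible, Probable or Definite.

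**Smaller grid as a cross-check:** non-transient, temporal, no rechallenge, four alternatives × improved or not = 8 cells. Common: definite alternative (2 cells) goes to level 1, and none with improvement (1) goes to Probable, leaving 8 − 3 = 5 without a level. Uncommon: definite (2) goes to level 1 and possible (2) to Possible, leaving 8 − 4 = 4 without a level.

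**Two further overlaps:** a common event with no other cause that improves off drug and recurs on rechallenge meets both Probable and Definite. An uncommon event with no temporal relationship and a probable alternative meets both Concurrent Condition and Remote.

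**Novel events:** if the event has not been reported for the drug, level 1 applies in the same way as for transience, whatever its timing.

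**The case against.** The strongest reply is that the consequence is small and partly inferred.

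- **Nothing is hidden.** A reader might infer that the reports conceal mild, unexpected or catheter-related harm. The documents do not support this. The three-monthly report includes all events by masked assignment, deaths and serious events are reported at once whatever their relationship, and section VIII.C compares the incidence of each event by Fisher's exact test without using attribution. This stands, and limits the point to the flag.
- **The link from scale to flag is not written down.** The protocol does not say how attributable is decided. This stands as to size. The five-level scale is, however, the only causality instrument in the protocol, so it is reasonable to assume that the flag rests on it. The missing mapping is itself part of the fault.
- **The examples are only examples.** The governing words are that the event is not related to study drug, and meeting one example does not force that rating. This stands against saying that all Mild events will be rated unrelated. It does not rescue examples that point the wrong way.
- **Gaps need not bias.** An event with no level may be placed either way. This stands: the gaps make the rating unreliable, and only the transience and novelty examples give a direction.
- **Dechallenge comes at the end of each course.** Both courses have fixed lengths, 30 and 60 days, and events are followed to a conclusion, so a persisting event can meet the dechallenge condition late. This narrows one gap. It does not help an event with a possible or probable alternative cause, or one that settles while dosing continues.
- **Catheter events.** A reader might infer that the scale miscodes catheter infection as unrelated. It does not. Section VII.A requires catheter-related events to be recorded and lists etiology as an item separate from relationship to study drug. A scale on medication rightly rates such an event as not due to the drug.

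**Conclusion.** The scale should be reworded. Two of its stated grounds for no relationship do not bear on causation, one of them coincides with the definition of Mild, and the five levels are neither exhaustive nor mutually exclusive. Under a literal reading, 13 of 18 non-transient profiles with a temporal relationship and no definite alternative cause have no level. Of the 18 transient counterparts, 13 are unrelated only and 5 are rated two ways.

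On the assumption that the report's flag is taken from this scale, the flag is unreliable in general and biased towards not attributable for transient and newly seen events. The size of that bias cannot be computed: the counts are of logical combinations, not of events, and the protocol does not map levels to attributable or not. Event recording, serious-event reporting and the final incidence comparison are unaffected.

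**What to change.** In section VII.A:

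1. Delete transience and absence of earlier reports from the examples under Concurrent Condition, leaving no temporal relationship or a definite alternative cause.
2. Drop the requirement that the event be uncommon for the drug class from Remote and Possible.
3. Redefine the levels so that every event fits exactly one. For example, a temporal relationship with a probable alternative cause is Remote. Any other temporal event that does not meet Probable or Definite and has no definite alternative cause is Possible. Let Definite take precedence over Probable. Send events with no temporal relationship to Concurrent Condition only, and those with a weak one and no definite alternative cause to Remote only.
4. State which levels count as attributable in the three-monthly report.

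Applied to the 18 combinations in the table, with transience no longer a criterion, this gives Definite 1, Probable 1, Possible 1 + 3 + 3 + 3 = 10 and Remote 3 + 3 = 6. The total is 18, with none unplaced and none placed twice.

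The cost is the rewording of one list and one added sentence, with the project officer's concurrence and the IRB review that section VII.D requires, and matching wording on the case report form if it prints the definitions. The downside is that more events will be listed as possibly related. No additional catheter field is needed.
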